7. PLANNED ANALYSIS

All analyses in this study are descriptive.

For categorical variables summary tabulations of the number and percentage within each category (with a category for missing data) of the parameter will be presented. For continuous variables number of values, mean, standard deviation, minimum, median, maximum and number of missing values will be presented. Incidence rates and 95% CI will be given when appropriate.

7.1 DEMOGRAPHIC AND OTHER BASELINE CHARACTERISTICS

Only descriptive statistics are planned for this section of the report. All baseline analyses will be done for the treated set.

7.2 CONCOMITANT DISEASES AND MEDICATION

Only descriptive statistics are planned for this section of the report. All analyses will be done for the treated set.

7.3 PRIMARY ENDPOINT

For the primary endpoint, the percentage of patients with therapeutic success will be presented together with the 95% confidence interval. The number and percentage of patients with and without therapeutic success will be calculated for the whole FAS set

The PF-10, represented by the physical functioning subscale of the Short Form 36 (SF-36), ranges from 0 to 100. A higher score indicates a better physical functioning. The score is calculated as followed:

Answer to questions 01- 10	Score
Yes, limited a lot	1
Yes, limited a little	2
No, not limited at all	3

Transformed scale = $[(\text{Sum of final item values} - 10) * 100] / 20$

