### **9.2 SETTING**

It is planned that data of approximately 1200 patients from approximately 225 sites in 6 countries will be collected. Site selection will be performed to reflect routine COPD care in the participating countries to secure representativeness of the COPD population. The following countries will participate in this non-interventional study: Belgium, Denmark, Sweden, The Netherlands, Luxembourg and Portugal.

A log of all patients included into the study (i.e. having given informed consent) will be maintained in the ISF at the investigational site irrespective of whether they have been treated or not.

Boehringer Ingelheim reserves the right to discontinue the study overall or at a particular study site at any time for the following reasons:

1. Failure to meet expected enrolment goals overall or at a particular study site
2. Emergence of any efficacy/safety information that could significantly affect continuation of the study, or any other administrative reasons, i.e. lack of recruitment
3. Violation of the protocol, the contract, or applicable laws and regulations for non-interventional studies, which could disturb the appropriate conduct of the NIS

The investigator / the study site will be reimbursed for reasonable expenses incurred in case of study termination (except in case of the third reason).

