### **9.2.1 Selection of Patient Population**

1200 patients with chronic obstructive pulmonary disease (COPD) in whom combination treatment with long-acting bronchodilators is indicated in accordance with the guidelines are to be observed in approx. 225 sites (hospital and non-hospital pulmonary medicine physicians and general practitioners) as part of this NIS. In the six participating countries (Belgium, Denmark, Sweden, The Netherlands, Luxembourg and Portugal), sites in urban as well as rural areas will be included. The nationwide distribution of the participating sites in the six countries and the number of patients enrolled are intended to ensure that the data collected are representative.

Possible contraindications are to be checked prior to treatment with Spiolto® Respimat®. See also the latest Summaries of Product Characteristics on Spiolto® Respimat®.

Every physician is to enrol the first consecutive patients he/she chooses to treat with Spiolto® Respimat®. The inclusion of four to six patients is planned per site.

The decision to treat will be taken independently of participation in this NIS and will be made before participation is considered.

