## **9.5 STUDY SIZE**

In a previous study, 205.426 with over 1000 patients treated with Spiriva® Respimat®, therapeutic success (i.e., 10-point increase in the PF-10 score between Visit 1 and Visit 2) was achieved in 61% of the patients.

However, in the present study a lower therapeutic success rate is expected as patients may be already on maintenance treatment at baseline. Assuming a 50% therapeutic success rate and a sample size of 1116 patients, the 95% confidence interval for the therapeutic success rate would be between 47.1% (lower limit) and 52.9% (upper limit).

To account for a 7% drop-out rate, the sample size becomes 1200 patients.

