### **9.7.2 Null and alternative hypotheses**

No formal hypothesis testing will be performed since this is a self-controlled study.

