#### Main analysis

For the primary outcome, the proportion of patients with therapeutic success will be presented together with the 95% confidence interval.

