#### 9.10.1.3 Records

Case Report Forms (eCRFs) for individual patients will be provided by the sponsor via remote data capture. All of the clinical data and site/investigator characteristics will be captured via a web-based Electronic Data Capturing system. The site staff will enter and edit the data via a secure network, with secure access features (username, password and secure identification – an electronic password system). A complete electronic audit trail will be maintained.

Patients must not be identified on the eCRF by name. Appropriately coded identification (i.e. Patient numbers) must be used.

All patient questionnaires will be paper-based and will be left at the site upon completion by the patient.

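### The planned precision and the 95% CI for therapeutic success treat patients as independent although about 225 sites enrol four to six each; the effect is modest and a low-priority SAP change would cover it

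*SAP*

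**What the plan says.** Protocol 9.5 sizes the study on precision alone. At a 50% success rate and 1116 patients, "the 95% confidence interval for the therapeutic success rate would be between 47.1% (lower limit) and 52.9% (upper limit". Allowing for 7% drop-out brings enrolment to 1200. No ICC or design effect is mentioned.

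The sample is grouped by site. Protocol 9.2 plans data on "approximately 1200 patients from approximately 225 sites in 6 countries", and Protocol 9.2.1 adds: "The inclusion of four to six patients is planned per site". The sites are described as "hospital and non-hospital pulmonary medicine physicians and general practitioners", in urban and rural areas.

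For the analysis, Protocol 9.7.1 defers details to the analysis plan. Protocol 9.7.3 (main analysis) says that "the proportion of patients with therapeutic success will be presented together with the 95% confidence interval", and SAP 7.3 says the same of the percentage in the full analysis set: "the percentage of patients with therapeutic success will be presented together with the 95% confidence interval". Neither names the CI method. SAP 6.5 declares pooling of centres not applicable, since centre and country are not part of the model. SAP 4 announces a 95% CI for the change in PF-10, but SAP 7.4 promises only summary statistics for that endpoint.

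Protocol 9.7.2 states: "No formal hypothesis testing will be performed since this is a self-controlled study". SAP 7 describes every analysis as descriptive.

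**The concern.** A binomial CI is correct when patients respond independently of one another. Patients at one site share a physician, inhaler training and a local case mix, and the sites range from general practice to hospital pulmonology. Some positive correlation of response within sites is therefore plausible. If it exists, the simple interval is too narrow and covers somewhat less than its stated 95%.

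Because no hypothesis is tested, the CI is the only statement of uncertainty about the primary outcome, and its planned width is the stated basis for 1200 patients. Protocol 9.2 and 9.2.1 also aim for representative data. Readers will therefore generalise beyond the enrolled sites, which makes between-site variation part of the uncertainty.

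**Working it through.** **Inputs from the documents.** Success rate p = 0.50, evaluable n = 1116, enrolled 1200, drop-out 7% (Protocol 9.5); about 225 sites (Protocol 9.2); four to six patients per site (Protocol 9.2.1). Mean evaluable patients per site: m = 1116/225 = 4.96.

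**Input that is assumed.** The ICC. The documents give none; 0.01, 0.02 and 0.05 are used as an illustrative range.

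**Step 1: reproduce the plan's figure.** Half-width = 1.96 × √(0.5 × 0.5/1116) = 2.933 points, so the interval is 47.07% to 52.93%, which rounds to the stated 47.1% to 52.9%. The Wilson interval is the same to two decimals; Clopper-Pearson gives 47.02% to 52.98%. Also 1116/0.93 = 1200. The plan's arithmetic is correct, and it is the independent-patient calculation.

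**Step 2: allow for clustering.** Design effect DE = 1 + (m − 1) × ICC = 1 + 3.96 × ICC. Half-width = 2.933 × √DE. Effective n = 1116/DE. Coverage of the simple interval = 2Φ(1.96/√DE) − 1.

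| Assumed ICC | DE | √DE | Half-width (points) | Increase | Effective n | Coverage of simple CI |
|---|---|---|---|---|---|---|
| 0 | 1.000 | 1.000 | 2.93 | – | 1116 | 95.0% |
| 0.01 | 1.040 | 1.020 | 2.99 | 0.06 | 1073 | 94.5% |
| 0.02 | 1.079 | 1.039 | 3.05 | 0.11 | 1034 | 94.1% |
| 0.05 | 1.198 | 1.095 | 3.21 | 0.28 | 932 | 92.7% |

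**Step 3: unequal sites.** The widest spread that keeps 225 sites, 1200 patients and four to six per site is 75 sites of four and 150 of six (300 + 900 = 1200). The mean of (m − 1) over patients is (75 × 4 × 3 + 150 × 6 × 5)/1200 = 4.5. With 7% random loss, DE = 1 + 0.93 × 4.5 × ICC = 1 + 4.185 × ICC. The half-widths are 2.99, 3.05 and 3.23 points, so unequal size within the planned range hardly matters.

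**Step 4: simulation of that layout.** Repeated simulations with at least 20,000 runs per ICC gave simple-CI coverage of 94.4–94.6% at ICC 0.01, 93.8–94.3% at 0.02 and 92.1–92.8% at 0.05. A site-clustered interval (linearised variance, t on sites minus one degrees of freedom) covered 94.7–95.2%. With the ICC near zero, its mean half-width was 2.947 against 2.932 points for the simple interval, a cost of 0.015 point.

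**Step 5: PF-10 change.** No SD is given, so only the ratio can be stated: the half-width of that CI would grow by the √DE column, a factor of 1.02, 1.04 or 1.09.

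**The case against.** The case for leaving the plan alone is strong on size. Over the assumed range the half-width grows by 0.06 to 0.28 points. At one decimal, an ICC of 0.01 or 0.02 turns 47.1–52.9% into 47.0–53.0%, the same as switching from Wald to Clopper-Pearson. The ICC may well be small: the PF-10 is completed by the patient, enrolment is consecutive, and the endpoint is a within-patient change. The small sites themselves limit the design effect. The SAP does not overlook centre; section 6.5 leaves it out openly, and section 7 calls everything descriptive. All of this stands, and it sets the priority.

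It does not remove the point. Section 6.5 concerns whether centre enters a model; it gives no reason to treat patients within a site as independent. A descriptive 95% CI still claims 95% coverage.

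Stronger readings are tempting and are not supported:

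- *The 47.1–52.9% is a miscalculation.* It reproduces exactly under independence.
- *The study is too small and must enrol more.* Any such number would rest wholly on an ICC that the documents do not give, and no test, power target or threshold has to be met.
- *Coverage is seriously wrong.* An ICC of 0.10 would give 3.47 points and 90.3% coverage, but nothing in the documents points to correlation that large.
- *Protocol 9.5 must be amended.* Protocol 9.10.1.1 requires ethics committee and authority approval for amendments, which is out of proportion to a caveat of this size.

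**Conclusion.** The concern holds in a limited form. The planned precision and the planned CI both rest on independence between patients, the sample is grouped into about 225 small sites, and no section of the protocol or SAP allows for correlation within them. For assumed ICCs of 0.01 to 0.05, the interval would be too narrow by about 0.06 to 0.28 points on a half-width of 2.93, with true coverage of about 94.5% down to 92.7%. Coverage drops below 94% at an ICC of roughly 0.02; the simulated values straddle 94% there, so no sharper cut-off should be quoted.

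The existence of the gap follows from the documents. Its size depends on the assumed ICC and would be near zero if sites barely differ. The estimated success rate does not change and no decision depends on the interval, so the priority is low.

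**What to change.** Change the SAP only:

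- **SAP 7.3:** report the 95% CI for therapeutic success with site as the variance cluster, by Taylor linearisation or an intercept-only GEE with robust variance. Show the simple binomial CI, with its method named, alongside for comparison with Protocol 9.5.
- **SAP 7.4:** specify the CI for PF-10 change that SAP 4 announces, and compute it in the same way.
- **A note in the SAP, without a protocol amendment:** the planned 47.1–52.9% assumes no within-site correlation. The half-widths of 2.99 to 3.21 points for assumed ICCs of 0.01 to 0.05 can be added.
- **SAP 6.5** can stay as it is, because a clustered variance does not put centre into the model.

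The cost is a revised SAP version and a few lines of SAS. No new data or patients are needed: Protocol 9.10.1.3 states that "All of the clinical data and site/investigator characteristics will be captured via a web-based Electronic Data Capturing system", and Protocol 9.7.4 already identifies removals by site and patient number. The downside is a slightly wider interval if the correlation is positive, and about 0.015 point of extra half-width if it is near zero.

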7.4 SECONDARY ENDPOINT(S)

All analysis will be descriptive and will be performed on FAS. For general condition of patients and patient's satisfaction with Spiolto[®] Respimat[®], the number and percentage of patients within each category will be displayed. For absolute changes in PF-10 score, summary statistics will be provided.

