### **9.7.3 Planned analyses**

All patients who have received at least one dose of Spiolto® Respimat® will be included in the analyses; this is the treated set. All analyses will be performed on the treated set (as-treated analysis). If patients have missing values for an outcome, those patients will be excluded for that outcome's analysis. For example, if a patient is missing the PF-10 score at Visit 1 and/or Visit 2, that patient will be excluded from the analyses for the primary endpoint of therapeutic success and the secondary endpoint of change in PF-10 from Visit 1 to Visit 2.

The assessment will be carried out using SAS® software. The statistical characteristics presented in the end-of-text tables will be N / mean / SD / min / median / max for continuous variables. Tabulations of relative and absolute frequencies will be presented for categorical variables. Incidence rates and 95% CI will be given when appropriate.

The analyses will relate to the following data:

- Patient demographics (age, gender, height, and weight);
- Comorbidities (main diagnosis and concurrent diagnosis according to MedDRA, version valid as at the time of database closure);
- COPD related and other concomitant medication (according to the WHO classification, version valid at the time of database closure)
- History of smoking
- Exacerbations
- Breathlessness based on mMRC score at Visit 1
- Physical Functioning based on PF-10 scores (therapeutic success at Visit 2); primary outcome
- Changes from Visit 1 to Visit 2 in the PF-10 score; secondary outcome
- Patient satisfaction with Spiolto® Respimat® at Visit 2 only; secondary outcome
- General condition of the patient: evaluated by the physician (Physician's Global Evaluation (PGE)); secondary outcome
- Adverse Drug Reactions (ADR & SADR), fatal AEs, pregnancies
- GOLD spirometric classification (1,2, 3, 4)
- GOLD patient groups (A, B, C, D)

- Details of treatment with inhaled respiratory agents before the study
- Details of treatment with respiratory agents during the study
- Reasons for ending treatment during the observation period
- Details of treatment continuation / discontinuation

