#### **9.7.4 Handling of missing data**

If less than half of the PF-10 questions are missing for a patient, the missing values will be replaced with the mean of the other values, then the PF-10 score will be calculated. If half or more than half of the PF-10 questions are missing, no score will be calculated and the PF-10 score will be marked as missing. No other missing data will be imputed. Every effort will be made to collect complete data at the specified time points.

Any removal from the analysis will be documented, stating the site and patient number as well as the reason for removal.

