4. CHANGES IN THE PLANNED ANALYSIS OF THE STUDY

- New analyses set, which is not mentioned in the protocol (Details are displayed in Section 6.3):
 - Full analysis set (FAS)

- Further additional analyses, which are not mentioned in the protocol (Details are displayed in Section 7.4)
 - 95% confidence intervals for changes from baseline in PF-10 score

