6.3 PATIENT SETS ANALYSED

Full analysis set (FAS): All screened patients with informed consent, date of registration, at least one documented administration of Spiolto[®] Respimat[®] and available PF-10 score at visit 1 and visit 2.

Treated set (TS): All screened patients with informed consent, date of registration and at least one documented administration of Spiolto[®] Respimat[®].

Table 6.3: 1 Patient sets analysed

Class of endpoint	Patient set	
	TS	FAS
Primary and secondary endpoints		X
Safety endpoints	X	
Demographic/baseline	X	

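### The SAP analyses PGE and patient satisfaction only in patients with paired PF-10 scores, where the protocol analyses each outcome separately on the treated set, and it gives no reason

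*SAP*

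**What the plan says.** Protocol 9.7.3 sets one population for everything: "All analyses will be performed on the treated set (as-treated analysis"). It handles missing data outcome by outcome: "If patients have missing values for an outcome, those patients will be excluded for that" outcome's analysis. Its example covers a patient without PF-10 at one or both visits: "that patient will be excluded from the analyses for the primary endpoint of therapeutic success and the secondary endpoint of change in PF-10" between the visits. PGE and satisfaction are not in that list.

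SAP 6.3 defines the treated set much as the protocol does. It then defines the FAS as the same patients with one further condition: "and available PF-10 score at visit 1 and visit 2". Table 6.3:1 assigns the FAS, and not the treated set, to the row "Primary and secondary endpoints". SAP 7.4 repeats this ("All analysis will be descriptive and will be performed on FAS") and goes on to name general condition and satisfaction. SAP section 4 lists the FAS under changes ("New analyses set, which is not mentioned in the protocol") and points to 6.3. Neither place gives a reason.

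Protocol 9.7.4 also requires a record of exclusions: "Any removal from the analysis will be documented, stating the site and patient number as well as the reason for removal".

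**The concern.** The two documents give different populations for PGE and satisfaction. A treated patient with a recorded PGE rating or a completed survey, but without paired PF-10 scores, is counted under the protocol and left out under the SAP.

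The forms are separate. According to Annex 3 of the protocol, the physician enters PGE directly in the eCRF. PF-10 and the satisfaction survey are patient-completed paper forms (protocol 9.10.1.3). A PF-10 with half or more of its items missing gets no score (SAP 6.6), so even a patient who attended both visits can fall outside the FAS.

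Recorded data are therefore set aside because a different form is missing or cannot be scored. The reported denominators and percentages depend on which document is followed. If patients without paired PF-10 differ in general condition or satisfaction, the FAS tables describe a selected group.

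**Working it through.** **1. The plan's own figures.** Protocol 9.5 assumes 50% success in 1116 patients. The 95% interval is 0.50 ± 1.96 × √(0.25/1116) = 0.50 ± 0.0293, or 47.1% to 52.9%, as stated. Allowing for 7% drop-out, 1116/0.93 = 1200, also as stated. Both reproduce. They concern the primary endpoint, and the planned loss is 1200 − 1116 = 84 patients.

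**2. Who is counted under each document.**

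| Treated patient | Outcome | Protocol 9.7.3 | SAP 6.3 and 7.4 |
|---|---|---|---|
| No paired PF-10 | Therapeutic success, PF-10 change | Excluded | Excluded |
| No paired PF-10, PGE recorded | PGE | Included | Excluded |
| No paired PF-10, survey recorded | Satisfaction | Included | Excluded |

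For the PF-10 endpoints the two rules select essentially the same patients. They part only on PGE and satisfaction.

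**3. Effect on a percentage.** Let k be the treated patients with the outcome recorded but no paired PF-10. Take the FAS as 1116 and let d be the difference in a category's percentage between FAS patients and these k patients. The dropped share is m = k/(1116 + k), and the FAS percentage differs from that in all recorded patients by m × d. The documents give neither k nor d. I assume d of 10 to 40 points.

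| k | m | Shift for d = 10 to 40 points |
|---|---|---|
| 0 | 0 | 0 |
| 23 | 23/1139 = 2.0% | 0.2 to 0.8 |
| 42 | 42/1158 = 3.6% | 0.4 to 1.5 |
| 84 | 84/1200 = 7.0% | 0.7 to 2.8 |

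**4. Which row fits which outcome.** The last row is an illustration for Visit 1 PGE. It needs every planned drop-out to be in the treated set, to have a baseline PGE and to lack paired PF-10. Treated-set membership is itself uncertain for patients who do not return: protocol 9.1 foresees consented patients who are not treated, and SAP 6.7 documents treatment at Visit 2. For Visit 2 PGE and satisfaction, k counts only patients who returned and lack a scorable PF-10 at one visit, so the upper rows are the relevant ones.

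**5. If the loss differs from 7%.** With 3% to 20% of 1200 lacking paired PF-10 (36 to 240 patients, assumed), and otherwise as for the last row, the Visit 1 PGE shift runs from 0.03 × 10 = 0.3 to 0.20 × 40 = 8.0 points.

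**6. Precision.** The 95% half-width at 50% is 2.93 points for n = 1116 and 2.83 for n = 1200. The gain in precision is therefore only about 0.10 points. The issue is selection.

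**The case against.** The SAP lists the FAS openly as a change, and its pointer leads to the table that assigns it. Protocol 9.7.1 leaves details to the analysis plan. SAP version 1.0 is dated 25 August 2017, before the planned end of data collection in March 2018, and no hypothesis is tested. All of this stands, so a reader who inferred a hidden or post hoc change would go beyond the documents. The change is disclosed but unexplained.

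A common cohort also has a merit for PGE, because the protocol abstract frames that objective as running from Visit 1 to Visit 2. With Visit 1 tabulated on 1200 patients and Visit 2 on 1116, drop-out alone could look like a change of 0.07 × d, or 0.7 to 2.8 points. That is as large as the shift at issue. The argument is fair, but a table of patients with both PGE ratings meets it directly and needs no PF-10 condition. It does not apply to satisfaction, which is measured once.

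Two numerical cautions also stand. The 84 comes from a planning assumption about drop-out and is not a ceiling on missing paired PF-10. And 2.8 points should not be read across to satisfaction or Visit 2 PGE: a patient who does not return has no Visit 2 rating or survey to lose, and the half-item imputation rule limits unscorable forms among those who do.

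Finally, moving to the treated set can mislead if the denominator is left open. SAP section 7 includes a category for missing data. With 84 missing, 80% satisfied among 1116 becomes 0.80 × 1116/1200 = 74.4% of all treated patients, a fall of 5.6 points caused by the denominator alone. The fix has to settle this.

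**Conclusion.** The point holds as a minor one. For two of the three secondary outcomes, the SAP replaces the protocol's outcome-by-outcome rule on the treated set with a condition on a questionnaire that those outcomes do not use, and gives no reason.

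The number affected cannot be taken from the documents. The clearest loss is in Visit 1 PGE, where the 7% illustration gives 0.7 to 2.8 points. That range rests on d of 10 to 40 points and on all 84 patients being treated and rated at baseline. At Visit 2 the loss is probably small and may be nil.

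A reader might infer that the primary result is biased by the new set. The documents do not support that: for therapeutic success and PF-10 change, the protocol's own rule already excludes patients without paired scores. Nor are the exclusions untraceable. Treated-set N minus FAS N gives their number, and the removal record in protocol 9.7.4 should identify them. Neither figure by itself says how many had a rating or survey on record. As all analyses are descriptive, no error rate or power is involved.

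**What to change.** In SAP Table 6.3:1 and 7.4:

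- Keep the FAS for therapeutic success and PF-10 change only.
- Tabulate satisfaction, and PGE at each visit, in treated-set patients with that outcome recorded. Use the number with a recorded value as the percentage denominator and show the number missing as a separate count outside it. This follows protocol 9.7.3.
- Add a table of PGE at Visit 1 and Visit 2 in patients with both ratings, so that drop-out does not appear as change.
- If the FAS is kept for PGE, state the reason in SAP section 4 and report how many recorded ratings it removes.

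The cost is SAP wording, a population flag and one extra table. Denominators will differ slightly between endpoints. No further data are needed.
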